5.3 Lifestyle Considerations

Not applicable.

5.4 Screen Failures

Screen failures are defined as patients who consent to participate in the clinical study but are not subsequently randomly assigned to study drug. A minimal set of information will be collected and is required to ensure transparent reporting of screen failure patients to meet the Consolidated Standards of Reporting Trials publishing requirements and to respond to queries from regulatory authorities.

Individuals who do not meet the criteria for participation in this study may be rescreened.

5.5 Criteria for Temporarily Delaying Randomization

Not applicable.

6 STUDY DRUGS AND CONCOMITANT THERAPY

Study drug is defined as any investigational intervention(s), marketed product(s), or placebo intended to be administered to a patient according to the study protocol beginning on Cycle 1 Day 1.

6.1 Study Drugs Administered

Intervention Name	Tamibarotene	Tamibarotene-matched Placebo	Azacitidine
Туре	Drug	Drug	Drug
Dose Formulation	Tablet	Tamibarotene-matched tablet	Reconstituted as solution or suspension
Unit Dose Strength(s)	2-mg tablets	Not applicable	100-mg single-use vials

Intervention Name	Tamibarotene	Tamibarotene-matched Placebo	Azacitidine
Dosage Level and Regimen	6 mg twice per day (BID); Days 8 through 28 of each 28-day treatment cycle See Section 6.2.1 for details of dose administration.	3 tablets that match tamibarotene BID; Days 8 through 28 of each 28-day treatment cycle See Section 6.2.1 for details of dose administration.	75 mg/m² once per day; Days 1 through 7 of each 28-day treatment cycle If dosing on Days 6 and 7 is not possible due to logistical limitations, these doses may be delayed to Days 8 and 9. See Section 6.2.2 for details of dose administration.
Route of Administration	Oral	Oral	Intravenous or subcutaneous
Use	Experimental	Placebo comparator	Background intervention
Investigational Medicinal Product (IMP) and Non- Investigational Medicinal Product (NIMP)	IMP	IMP	IMP
Sourcing	Provided centrally by the sponsor	Provided centrally by the sponsor	As regionally applicable
Packaging and Labeling	Study drug will be provided in bottles. Each bottle will be labeled as required per country requirement.	Study drug will be provided in bottles. Each bottle will be labeled as required per country requirement.	Study drug is commercially available and will be provided in the commercial packaging. Each container will be labeled as required per country requirement.

6.2 Preparation/Handling/Storage/Accountability

6.2.1 Tamibarotene/Placebo

A total of 6 tablets (12 mg total) will be taken each day, 3 tablets (6 mg) in the morning and 3 tablets (6 mg) in the evening. Patients will be instructed to take the dose with a glass of water after their morning meal and after their evening meal. Tablets should not be crushed, broken, or split. Dosing should not be repeated if a patient vomits. A dose missed by greater than 4 hours should be skipped.

Until dispensed to the patients, the study drug will be stored in a securely locked area, accessible to authorized personnel only. Tablets should be stored at room temperature (15°C to 30°C) and should not be removed from the bottles until immediately before administration.

The investigator or designee must confirm appropriate temperature conditions have been maintained during transit for all tamibarotene/placebo received, and any discrepancies are reported and resolved before its use.

Only patients enrolled in the study may receive tamibarotene/placebo and only authorized site staff may supply or administer it. All tamibarotene/placebo must be stored in a secure, environmentally controlled, and monitored (manual or automated) area in accordance with the labeled storage conditions with access limited to the investigator and authorized site staff.

The investigator, institution, or the head of the medical institution (where applicable) is responsible for tamibarotene/placebo accountability, reconciliation, and record maintenance (i.e., receipt, reconciliation, and final disposition records).

Further guidance and information for the final disposition of unused tamibarotene/placebo are provided in the Pharmacy Manual.

6.2.2 Azacitidine

Azacitidine is commercially available as a lyophilized powder. The product is reconstituted as a suspension for subcutaneous injection or as a solution with further dilution for intravenous infusion.

Unreconstituted vials should be stored at room temperature (15°C to 30°C). Refer to the azacitidine package insert approved by your National Regulatory Agency/Competent Authority for complete details, as applicable (e.g., VIDAZA USPI, VIDAZA SmPC).

6.3 Measures to Minimize Bias: Randomization and Blinding

Randomization will be double-blinded and will be performed on Cycle 1 Day 1 using an interactive response system. ¹

Approximately patients with HR-MDS will be randomly assigned to study drug. Patients will be randomized 2:1 to receive either tamibarotene plus azacitidine or placebo plus azacitidine. Randomization will be stratified by the IPSS-R risk group (Intermediate, High, and Very High Risk). In addition, stratification of analyses by geographical region (North America, Western Europe, and Israel versus Eastern Europe) will be performed, as there may be differences in available supportive care treatments and in access to subspecialty consultants and specialized hospital care among these regions. Block randomization with a block size of 6 will be used.

All patients, investigators, pharmacist(s) performing drug preparation, and site staff will be blinded to treatment assignment.

Personnel responsible for the bioanalysis of the tamibarotene concentrations in plasma will be provided with the randomization code in order to identify samples for analysis. The results will not be shared with the sponsor until the study is unblinded.

36

¹ Patients can be randomized earlier than Cycle 1 Day 1, but within 72 hours of the first dose of study drug, to accommodate operational needs.

In addition, at the time of CR futility analysis, preliminary PK analysis will be performed by designated contract research organization (CRO), the limited personnel from the CRO will have access to the unblinded PK data to build the population PK model.

The interactive response system will be programmed with blind-breaking instructions.

In case of an emergency, the investigator has the sole responsibility for determining if unblinding of a patient's intervention assignment is warranted. Patient safety must always be the first consideration in making such a determination. If necessary, for patient safety, the investigator may unblind the patient's intervention assignment immediately, without prior discussion with the sponsor. The investigator may, at the investigator's discretion, contact the sponsor to discuss the situation prior to unblinding a patient's intervention assignment, unless this could delay emergency treatment for the patient. Maintaining the blinded treatment assignment will preserve integrity of the study data. If a patient's intervention assignment is unblinded without discussion with the sponsor, the sponsor must be notified within 24 hours of this occurrence. The date and reason that the blind was broken will be recorded.

Sponsor safety staff may unblind the study drug assignment for any patient with a SAE if necessary. If the SAE requires that an expedited regulatory report be sent to one or more regulatory agencies, a copy of the report, identifying the patient's study drug assignment, may be sent to the investigators in accordance with local regulations and/or sponsor policy. Contact information for the Pharmacovigilance group is provided in Appendix 3.

6.4 Study Drug Compliance

Tamibarotene/placebo may be administered at the site or self-administered at home.

Azacitidine (subcutaneous or intravenous) will be administered under the supervision of the study site staff or trained designee (as needed).

When the study drug is administered at the site, patients will receive study drug directly from the investigator or designee, under medical supervision. The date and time of each dose administered in the clinic will be recorded in the source documents.

Compliance with tamibarotene/placebo will be assessed at each applicable study visit (Section 1.3). Patients will maintain diaries to include the date and time each dose of study drug is taken, including hour and minute. Patients are required to return the bottle(s) and unused study drug at each applicable study visit (Section 1.3). If a tablet is damaged (broken, crushed, split, etc.), the patient should record the information in the diary and bring the damaged tablet to the next study visit. The diaries, unused study drug, and study drug bottle will be used to assess study drug compliance and accountability.

A record of the quantity of study drug dispensed to and administered by each patient must be maintained and reconciled with study drug accountability records. Study drug start and stop dates, including dates for study drug delays and/or dose reductions, will also be recorded.

6.5 Dose Modification and Management of Toxicities

The instructions provided in Table 1 and Table 2 must be followed to adjust tamibarotene/placebo or azacitidine dosing for management of toxicities.

It is not anticipated that tamibarotene dose modifications would be needed for hematologic events (i.e., cytopenias, complications associated with cytopenias [including infection], or bleeding). Consideration for relatedness should be given to the timing of the AE, the temporal association between the onset of the AE and the administration of azacitidine (Days 1 through 7) and tamibarotene (Days 8 through 28), and the known adverse reactions for tamibarotene (see IB) and azacitidine (see most current VIDAZA USPI/VIDAZA SmPC, or applicable locally approved labeling).

Table 1: Dose Modifications

Adverse Events (AEs)	Dosage Modification			
Hematologic toxicity	The dose of azacitidine should be modified as described in the most current VIDAZA USPI/VIDAZA SmPC or applicable locally approved labeling.			
	If Grade 4 hematologic toxicity does not resolve after azacitidine dose modifications have been attempted, the dose of tamibarotene may be CCI.			
Retinoic acid syndrome	Hold tamibarotene/placebo until RAS is considered controlled and Grade ≤2.			
(RAS) ^a	See Section 6.8.9 for additional information on monitoring and treatment of RAS.			
Grade 4 hypertriglyceridemia	Hold tamibarotene/placebo until AE resolves to Grade ≤1 or baseline. Tamibarotene/placebo treatment may resume at the previous dose level once the AE has resolved to Grade ≤1 or baseline. Should the same AE recur, the dose of tamibarotene/placebo will be CCI Dosing may be CCI if the AE remains Grade ≤1 or at baseline for 14 days.			
Serum electrolyte and renal toxicity	The dose of azacitidine should be modified as described in the most current VIDAZA USPI/VIDAZA SmPC or applicable locally approved labeling.			
	If serum electrolyte and renal toxicity does not resolve after azacitidine dose modifications have been attempted, the dose of tamibarotene may be CCI.			
Grade ≥3 non-hematologic toxicity (excluding hypertriglyceridemia and serum electrolyte and renal toxicity)	Hold tamibarotene/placebo, if AE is deemed related to tamibarotene and not resolved with supportive care, until AE resolves to Grade ≤1 or baseline. Tamibarotene/placebo treatment may resume at the previous dose level once the AE has resolved to Grade ≤1 or baseline. Should the same AE recur, the dose of tamibarotene will be CCI . Dosing may be if the AE remains Grade ≤1 or at baseline for 14 days.			
	If Grade ≥3 non-hematologic toxicity does not resolve after dose modification to tamibarotene/placebo has been attempted, azacitidine may be held until AE resolves to Grade ≤1 or baseline.			
All and G. B.C. Co	If attribution is unclear, follow tamibarotene dose modification first. If AE does not resolve, azacitidine modifications may be attempted next.			

Abbreviations: SmPC = Summary of Product Characteristics; USPI = United States Prescribing Information.

Note: Tamibarotene administration should not be resumed in the case of ≥28-day dose delay due to treatment-related AEs.

Table 2: Dose Reductions of Tamibarotene/Placebo

Dose Level	Tamibarotene/Placebo Dose	
Initial Dose: Level 0	6 mg twice per day (BID)	
CCI	CCI	
CCI	CCI	

^a Also referred to as differentiation syndrome.

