6.8.9 Retinoic Acid Syndrome

Patients should be carefully monitored for the development of retinoic acid syndrome (RAS). High-dose dexamethasone (i.e., 10 mg/m^2 intravenous twice daily), and supportive measures (e.g., diuretics, dialysis, mechanical ventilation) as needed, should be implemented at the earliest suspicion of RAS. Glucocorticoid therapy should continue until complete disappearance of symptoms and then tapered. Tamibarotene/placebo therapy should be temporarily discontinued until RAS is considered controlled and <Grade 2.

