10.3.3 Recording and Follow-up of AE and/or SAE

AE and SAE Recording

- When an AE/SAE occurs, it is the responsibility of the investigator to review all documentation (e.g., hospital progress notes, laboratory reports, and diagnostics reports) related to the event.
- The investigator will then record all relevant AE/SAE information.
- It is **not** acceptable for the investigator to send photocopies of the patient's medical records to the Pharmacovigilance group in lieu of completion of the SAE required form.
- The investigator will attempt to establish a diagnosis of the event based on signs, symptoms, and/or other clinical information. Whenever possible, the diagnosis (not the individual signs/symptoms) will be documented as the AE/SAE.

Assessment of Severity

The investigator will make an assessment of severity (Grades 1 through 5) for each AE and SAE reported during the study using National Cancer Institute CTCAE, version 5.

An event is defined as 'serious' when it meets at least 1 of the predefined outcomes as described in the definition of an SAE, NOT when it is rated as severe.

Assessment of Causality

- The investigator is obligated to assess the relationship between study drug and each occurrence of each AE/SAE.
- Related assessment is reported when a "reasonable possibility" of a relationship conveys that there are facts, evidence, and/or arguments to suggest a causal relationship, rather than a relationship cannot be ruled out.
- The investigator will use clinical judgment to determine the relationship.
- Alternative causes, such as underlying disease(s), concomitant therapy, and other risk factors, as well as the temporal relationship of the event to study drug administration, will be considered and investigated.
- The investigator will also consult the IB and/or Product Information, for marketed products, in his/her assessment.
- There may be situations in which an SAE has occurred, and the investigator has minimal information to include in the initial report to the Pharmacovigilance group. However, it is very important that the investigator always makes an assessment of causality for every event before the initial transmission of the SAE data to the Pharmacovigilance group. It is helpful if the investigator includes the rationale for the assessment as being causally related, or not causally related, in the transmission of the SAE data.

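### Protocol Table 1 and Section 6.8.9 set different grades for restarting tamibarotene/placebo after retinoic acid syndrome (RAS), and nothing expressly says which prevails

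*Protocol*

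**What the plan says.** Protocol Section 6.5 makes its dosing tables mandatory: "The instructions provided in Table 1 and Table 2 must be followed to adjust tamibarotene/placebo or azacitidine dosing for management of toxicities". For RAS, Table 1 reads: "Hold tamibarotene/placebo until RAS is considered controlled and Grade ≤2". The same row then adds: "See Section 6.8.9 for additional information on monitoring and treatment of RAS".

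Section 6.8.9, under Concomitant Therapy, covers RAS monitoring and treatment and also gives a restart condition: "Tamibarotene/placebo therapy should be temporarily discontinued until RAS is considered controlled and <Grade 2".

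A separate Table 1 row is headed "Grade ≥3 non-hematologic toxicity (excluding hypertriglyceridemia and serum electrolyte and renal toxicity", with those two exclusions and no others. Its instruction is: "Hold tamibarotene/placebo, if AE is deemed related to tamibarotene and not resolved with supportive care, until AE resolves to Grade ≤1 or baseline". That row goes on to say what happens if the same event recurs, with part of the text redacted. The RAS row has no recurrence provision.

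Two other passages bear on the point. On grading, Section 10.3.3 says: "The investigator will make an assessment of severity (Grades 1 through 5) for each AE and SAE reported during the study". A note under Table 1 says: "Tamibarotene administration should not be resumed in the case of ≥28-day dose delay due to treatment-related AEs".

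**The concern.** Both RAS passages concern the same drug, the same event and the same requirement that RAS be considered controlled. They differ only in the grade at which the hold ends. A site that works from Table 1 and a site that works from Section 6.8.9 can therefore treat the same patient in opposite ways while each follows the protocol as written.

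Section 6.8.9 calls for high-dose dexamethasone at the earliest suspicion of RAS, and for dialysis or mechanical ventilation where needed. The restart threshold is thus a patient-safety instruction. It affects when patients are re-exposed, how long dosing is interrupted and how much tamibarotene they receive. Through the 28-day note it can also affect whether tamibarotene is resumed at all.

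Section 8 of the protocol rules out waivers and exemptions, so a site cannot settle the question by exemption.

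**Working it through.** No arithmetic applies. The check takes each rule literally and applies it to each whole grade of RAS that is considered controlled.

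| Current grade | Table 1, RAS row | Section 6.8.9 | Table 1, Grade ≥3 non-hematologic row, if it applies |
|---|---|---|---|
| 1 | restart allowed | restart allowed | restart allowed |
| 2 | restart allowed | hold | hold, unless baseline was already Grade 2 or above |
| 3 or 4 | hold | hold | hold, unless baseline was already at that grade |

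**Step 1: the two RAS passages.** They agree at Grade 1 and at Grades 3 and 4. They disagree only at controlled Grade 2.

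**Step 2: is there a precedence rule?** Section 6.5 says Tables 1 and 2 must be followed, which favours Table 1. But the RAS row itself sends the reader to Section 6.8.9, and that section states its own restart condition. No sentence says which governs if they differ.

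**Step 3: does the length of the hold matter?** Under Section 6.8.9 the hold lasts until RAS falls below Grade 2. Under Table 1 it can end at Grade 2. If the extra time takes a treatment-related delay to 28 days or more, the note under Table 1 says tamibarotene should not be resumed. The documents do not give the time RAS takes to move from Grade 2 to Grade 1, so how often this would happen is unknown.

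**Step 4: the Grade ≥3 non-hematologic row.** It applies only if the event reached Grade ≥3, is deemed related to tamibarotene and was not resolved with supportive care. Its exclusions cover two toxicities that have rows of their own, hypertriglyceridemia and serum electrolyte and renal toxicity. RAS also has its own row but is not excluded. On the text it is open whether severe, related, unresolved RAS falls under the RAS row alone or under both rows. If both apply, they differ at Grade 2, and only the general row has a recurrence provision.

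**Step 5: how many cut-offs?** On whole grades, below Grade 2 is the same as Grade ≤1. The three passages therefore contain two cut-offs. The general row differs from Section 6.8.9 only in allowing return to baseline as an alternative and in not requiring that RAS be considered controlled.

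**The case against.** **The sign may be a reading error.** The core mismatch turns on one character, and a ≤ that lost its underline would read as <. Signs are inconsistent elsewhere in the text: the Hwang-Shih-DeCani gamma is 4 in the protocol synopsis and -4 in Section 9.5, and the ECOG inclusion limit reads <2 while SAP Sections 7.3.3 and 7.4.7.3 plan categories for ECOG 2 and 3. This is a good reason to check the source PDF before acting. For this particular character it remains conjecture, and as the text stands the passages conflict. If Section 6.8.9 did prove to say ≤, the main contradiction would disappear and the question about the general row would remain.

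**Table 1 arguably governs.** It is mandatory, its RAS row cites Section 6.8.9 only for monitoring and treatment, and Section 6.8.9 uses the word should. This gives a site a reasonable basis for following Table 1. For that reason, a reader who infers that either action is automatically a protocol deviation goes too far. But the precedence is only implied, and Section 6.8.9 still states a different threshold.

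**The general row may not reach RAS.** A dedicated row is ordinarily read as overriding a catch-all. The two listed exclusions also have their own explanation: the hypertriglyceridemia row acts only at Grade 4, and the electrolyte and renal row modifies azacitidine first, so without the exclusions the general row would cut across both. This objection largely stands. The missing exclusion shows an ambiguity. It does not show that the general row was meant to cover RAS.

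**Conclusion.** The contradiction between Table 1 and Section 6.8.9 is literal. It is confined to RAS that is controlled and at Grade 2, where one passage allows restart and the other requires a continued hold. The conclusion assumes that the inequality signs are as they appear in the text and that grades are whole numbers. It affects no estimand, test or sample size. It matters because it concerns re-exposure after a potentially severe toxicity and can interact with the 28-day note.

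The general row is a secondary ambiguity, limited to RAS that reached Grade ≥3, is related to tamibarotene and was not resolved with supportive care. A reader might infer that every patient at Grade 2 is held by two passages and released by one. The documents do not support that, because the general row's conditions are not met by every such patient and its reach over RAS is itself unclear.

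A reader might also try to count the patients affected, for example by applying an assumed RAS rate to two thirds of the 190 patients in Protocol Section 9.4.2 (2/3 × 190 ≈ 127). That does not work. The documents give no RAS rate. The 190 is tied to the CR analysis, while SAP Section 7.4.3.1 places that analysis in the first participants out of a larger planned total, so 127 is not established as the arm size. Such a count would also include all RAS, not only RAS that is controlled at Grade 2. The number affected cannot be determined.

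**What to change.** 1. Check the inequality sign in Section 6.8.9, and the one in the RAS row of Table 1, against the source PDF.
2. If they differ as read here, reconcile the two passages so that both state one identical restart threshold.
3. State in Table 1 which row governs Grade ≥3 RAS, including whether the general row's recurrence provision applies to it.

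The sponsor's clinical team must decide the threshold and the governing row. Neither is proposed here. Simply adding RAS to the general row's exclusions would already choose between clinical rules, so that too is theirs to decide.

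The cost is a wording change in Table 1 and Section 6.8.9, by amendment or clarification letter. It adds no procedures, visits or patients and leaves the statistical design unchanged.
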